performed first, within 14 days (window of +7 days) after the last dose of study intervention or decision to discontinue intervention. A safety follow-up visit will take place 30 days (window of +7 days) after the last administration of study intervention, and additionally, 90 days (window of +7 days) after the last administration of pembrolizumab. Efficacy follow-up visits will take place for participants who discontinued study intervention for reasons other than radiologically confirmed progressive disease (PD), death, withdrawal of consent, or lost to follow-up. These visits include tumor assessments, study intervention-related toxicity/AEs, and information about subsequent anti-cancer therapy. Active follow-up will be terminated by radiological PD, the start of a new anti-cancer treatment, death, withdrawal of consent for further participation, or lost to follow-up.

After completion of the active follow-up period, participants will enter the long-term follow-up period. Participants will be followed for survival status and subsequent anti-cancer therapy by a telephone call at 3-month intervals (\pm 14 days) until the end of the study, withdrawal of consent, lost to follow-up, or death, whichever comes first.

Data Monitoring Committee: Not applicable

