4.1.1.3 Active Follow-up

A mandatory safety follow-up visit will take place 30 days (window of +7 days) after the last administration of the last study intervention (regorafenib and/or pembrolizumab).

If applicable, an additional safety follow-up must occur 90 days (window of +7 days) after the last pembrolizumab administration. Longer safety follow-up for pembrolizumab is required due to the long half-life of the antibody. Note: If pembrolizumab is permanently discontinued first and the day 30 or the day 90 safety follow-up visit after the last infusion of

Page 38 of 141

pembrolizumab falls into the regorafenib treatment period or regorafenib day 30 safety follow-up visit, no separate pembrolizumab day 30 or day 90 safety follow-up visit is necessary as the information gathering and examinations will occur with regorafenib treatment cycle visit, EoT visit, or day 30 safety follow-up visit. If regorafenib is discontinued first and the day 30 safety follow-up visit falls into pembrolizumab treatment or pembrolizumab day 30 follow-up visit, no separate regorafenib safety follow-up visit is necessary.

All pregnancies and exposure during breastfeeding should be collected from the start of study intervention through 120 days following discontinuation of study intervention, or 30 days following discontinuation of study intervention if the participant initiates new anti-cancer therapy.

Participants who discontinue study intervention due to radiologically confirmed PD will complete the mandatory safety follow-up visits.

Participants who discontinue from the study for any reason other than PD (or death, withdrawal of consent, or lost to follow-up) will be followed for progression during the active follow-up period. During the active follow-up period, computed tomography (CT) / magnetic resonance imaging (MRI) evaluations will be performed at efficacy follow-up visits (see the SoA in Section 1.3.1). In addition, study intervention-related toxicity/AE, information about survival status, and subsequent anti-cancer therapy will be followed up until completion of the active follow-up.

Active follow-up will be terminated by radiological PD, or the start of a new anti-cancer treatment, or death, or withdrawal of consent for further participation, or lost to follow-up.

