7.1.1 Withdrawal Criteria

7.1.1.1 Withdrawal from Study Intervention Period

Participants MUST be withdrawn from the study intervention if any of the following occurs:

- At their own request or at the request of their legally acceptable representative (if acceptable by local law). At any time during the study and without giving reasons, a participant may decline to participate further. The participant will not suffer any disadvantage as a result.
- If, in the investigator's opinion, continuation of the study intervention would be harmful to the participant's well-being.
- Progressive disease as per RECIST 1.1; however, treatment beyond radiological progression per iRECIST is possible if the participant is still benefiting from treatment.
- Clinical progression (every effort should be made to obtain radiological confirmation of disease progression [PD] during active follow-up). Note: In cases where radiographic evaluation is not possible, clinical progression may be used. Clinical progression is based on the judgment of the investigator (e.g., defined as worsening of the ECOG PS ≥3 or symptomatic deterioration including increase in liver function tests).
- The development of a second primary malignancy that requires a different treatment.
- Development of any intercurrent illness or situation which may, in the judgment of the investigator, affect assessments of clinical status and study endpoints to a relevant degree.
- Severe allergic reactions, such as exfoliate erythroderma, anaphylaxis, or vascular collapse.
- Start of a new anti-cancer therapy.

Page 77 of 141

- Use of illicit drugs or other substances that may, in the opinion of the investigator or their designated associate(s), have a reasonable chance of contributing to toxicity or otherwise confound the results.
- Pregnancy.
- Participant lost to follow-up.
- Death.

Participants MAY be withdrawn from the study intervention for the following reasons:

- At the specific request of the sponsor and in liaison with the investigator (e.g. obvious non-compliance, safety concerns).
- Participants should be taken off study intervention for disease progression. However,
 if a participant has radiographic progression but is achieving a clinically meaningful
 benefit, an exception to continue study intervention may be considered following
 consultation with the sponsor.

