7.2 Participant Discontinuation/Withdrawal from the Study

A participant must be withdrawn from the study at any time at his/her own request or at the request of their legally acceptable representative (if acceptable by local law).

A participant may be withdrawn from the study at any time at the discretion of the investigator for safety, behavioral, compliance, or administrative reasons. This is expected to be uncommon.

If the participant withdraws consent for disclosure of future information, the sponsor may retain and continue to use any data collected before such a withdrawal of consent.

If a participant withdraws from the study, and additionally requests destruction of her/his samples taken but not yet tested, the investigator must document this (either destruction by site or request to central lab, as applicable) in the site study records.

Withdrawal from active follow-up

Participants MUST be withdrawn from active follow-up if any of the following occurs:

- At their own request or at the request of their legally acceptable representative (if acceptable by local law). At any time during the study and without giving reasons, a participant may decline to participate further. The participant will not suffer any disadvantage as a result.
- Radiologically confirmed PD is observed and/or clinical progression (for participants who discontinued study intervention before PD due to any other reason).
- Start of subsequent systemic anti-cancer treatment.
- Development of a second primary malignancy that requires a different treatment.
- Substantial non-compliance with the requirements of the study.
- If, in the investigator's opinion, continuation of the active visits would be harmful to the participant's well-being.
- Participants lost to follow-up.
- Death.

Participants MAY be withdrawn from active follow-up if any of the following occurs:

• At the specific request of the sponsor and in liaison with the investigator (e.g. obvious non-compliance).

Withdrawal from long-term follow-up

Participants MUST be withdrawn from long-term follow-up if any of the following occurs:

• Withdrawal of consent to long-term follow-up.

Page 79 of 141

- Participants lost to follow-up.
- Death.

Participants MAY be withdrawn from long-term follow-up if any of the following occurs:

• At the specific request of the sponsor and in liaison with the investigator (e.g. obvious non-compliance).

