If bone metastases are known or suspected, a whole-body bone scan with both anterior and posterior projection using a technetium-99m-labeled phosphonate tracer (methylene diphosphonate (MDP), hydroxymethylene diphosphonate (HMDP), hydroxyethylene diphosphonate (HDP), or 2,3-dicarboxypropane-1,1-diphosphonate (DPD)) should be performed at screening. Bone scans should be repeated when CR or PR is identified in the CT/MRI assessments to confirm the absence of new bone lesion(s) disease or when progression in bone is suspected. A newly-detected bone lesion on bone scan should be confirmed by radiologic assessment (X-ray, CT, MRI if not already evident on the CT/MRI tumor assessment scans).

For consistency, the same imaging modality and equivalent technique (e.g. contrast agent, slice thickness, field of view, protocol, sequence, phosphonate tracer) should be used for all scans and tumor assessments across all time points performed on an individual participant, including screening/baseline scans.

Initial tumor imaging:

The time points for CT/MRI scans are described in the SoA (Section 1.3.1). A baseline radiological tumor assessment will be conducted within 28 days before the start of study treatment. Scans performed as standard of care that were obtained prior to the participant signing the informed consent may be used for the baseline tumor assessment, provided that they were performed within 42 days of starting study intervention and meet this protocol's imaging requirements. The investigator must review screening images to confirm the participant has measurable disease per RECIST 1.1 and to determine this participant's eligibility.

Tumor imaging on study:

Following treatment initiation, regardless of potential dose delays for either drug, subsequent tumor assessments will occur every 6 weeks with a maximum window of \pm 7 days during the first 54 weeks and every 9 weeks \pm 7 days thereafter.

Page 82 of 141

For participants who discontinue study treatment without confirmed radiological disease progression, the investigator should perform a complete physical, laboratory, and radiological assessment as soon as possible. Every effort should then be made to continue to perform tumor assessments every 6 weeks \pm 7 days during the first 54 weeks and every 9 weeks \pm 7 days thereafter. Imaging assessments will continue to be performed until whichever of the following occurs first:

- Investigator-assessed disease progression is confirmed

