9.4.1.3 Secondary Efficacy Endpoints

The secondary efficacy endpoints in this study are DOR as per RECIST 1.1 by investigator assessment and central review and ORR as per RECIST 1.1 by investigator assessment.

DOR (for PR and CR) is defined as the time (in days) from the first documented objective response of PR or CR, whichever is noted earlier, to disease progression or death (if death

Page 95 of 141

occurs before progression is documented). DOR will be defined for responders only, i.e. participants with a CR or PR. The actual dates the tumor scans were performed will be used for this calculation. DOR for participants who have not progressed or died at the time of analysis will be censored at the date of their last tumor evaluation.

The analysis will be done on the Full Analysis Set. In the pilot phase, the analysis will be done by cohort. In the expansion phase, the analysis will be done on participants who received the first line treatment determined in the pilot phase of the study.

For analyses of the secondary endpoints, proportion-based efficacy variables will be using frequency tables as well as 95% two-sided Clopper-Pearson confidence intervals. With regard to time to event data, these will be summarized descriptively using Kaplan Meier methodology and plots, as well as median estimates based on Greenwood's formula, including 95% two-sided confidence interval.

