The duration of overall response is measured from the time measurement criteria are first met for CR/PR (whichever is first recorded) until the first date that recurrent or progressive disease is objectively documented (taking as reference for progressive disease the smallest measurements recorded on study).

The duration of overall complete response is measured from the time measurement criteria are first met for CR until the first date that recurrent disease is objectively documented.

Stable disease duration

Stable disease is measured from treatment allocation until the criteria for progression are met, taking as reference the smallest sum on study (if the baseline sum is the smallest, this is the reference for calculation of PD).

The following text descriptions of the visit response are logically equivalent to the tables below.

Page 116 of 141

Table 10-5: RECIST	.1: Response for Participants with Target and Nor	n-target
Lesions		

Target Lesions	Non-Target Lesions	New Lesions	Overall	Best Response for this
			Response	category also requires
CR	CR	No	CR	
CR	Non-CR/Non-PD	No	PR	
CR	Not evaluated	No	PR	
PR	Non-PD or not all evaluated	No	PR	
SD	Non-PD or not all evaluated	No	SD	documented at least 6 weeks from treatment allocation
Not all evaluated	Non-PD	no	NE	
PD	Any	Yes or No	PD	
Any	PD	Yes or No	PD	
Any	Any	Yes	PD	

CR = complete response; NE = non-evaluable; PD = progressive disease; PR = partial response; RECIST = Response Evaluation Criteria in Solid Tumors; SD = stable disease

Participants with a global deterioration of health status requiring discontinuation of intervention without objective evidence of disease progression at that time should be reported as "symptomatic deterioration". Every effort should be made to document the objective progression even after discontinuation of intervention.

Table 10-6: RECIST 1.1: Response for Participants with Non-target Lesions Only

Non-Target Lesions	New Lesions	Overall Response
CR	No	CR
Non-CR/Non-PD	No	Non-CR/non-PD*
Not evaluated	No	NE
Unequivocal PD	Yes or No	PD
Any	Yes	PD

CR = complete response; NE = non-evaluable; PD = progressive disease; RECIST = Response Evaluation Criteria in Solid Tumors

Methods of Measurement

The same method of assessment and the same technique should be used to characterize each identified and reported lesion at baseline and during follow-up. All measurements must be recorded in millimeters (or decimal fractions of centimeters), if applicable.

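### Protocol Section 7.2 ends active follow-up at clinical progression for participants already off treatment, while the synopsis, 4.1.1.3 and 8.1 keep imaging them, so duration of response can miss progressions

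*Protocol*

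**What the plan says.** Section 7.2 lists events after which participants must leave active follow-up. One is "Radiologically confirmed PD is observed and/or clinical progression (for participants who discontinued study intervention before PD due to any other reason"). The and/or makes clinical progression sufficient without imaging.

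Other sections describe the same period differently:

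- The synopsis (Section 1.1) says "Efficacy follow-up visits will take place for participants who discontinued study intervention for reasons other than radiologically confirmed progressive disease (PD"), death, withdrawn consent or loss to follow-up.
- Section 4.1.1.3 says "Active follow-up will be terminated by radiological PD, or the start of a new anti-cancer treatment, or death", and adds consent withdrawal and loss to follow-up. Clinical progression is not named.
- Section 8.1 continues scans after treatment stops until the earliest of several events. The progression event is "Investigator-assessed disease progression is confirmed"; the others are new anti-cancer treatment, consent withdrawal, death and study end.
- Section 7.1.1.1, on stopping treatment for clinical progression, says "every effort should be made to obtain radiological confirmation of disease progression [PD] during active follow-up".
- The note to Table 10-5 (Section 10.5.1), on symptomatic deterioration that requires stopping, says "Every effort should be made to document the objective progression even after discontinuation of intervention".

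Under Section 9.4.1.3, DOR runs from first response to progression or death, and participants with neither "will be censored at the date of their last tumor evaluation". Section 10.5.1 ends a response at objectively documented recurrence or progression. SAP v3.0 Section 5.4.1.2 only lists DOR. SAP v3.0 Section 5.5.2 plans Kaplan-Meier summaries of PFS with rates at 6, 12, 18 and 24 months, but refers to SAP v2.0, which was not supplied, for the endpoint definitions.

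**The concern.** Active follow-up is the only period after treatment with scheduled scans. Long-term follow-up (Section 4.1.1.4) can be conducted by telephone. Two sites reading different sections would treat the same participant differently: one continues the scans, the other stops them when the participant deteriorates. Under the second reading imaging stops because the participant is getting worse, so the censoring is informative. DOR by central and by investigator assessment is a secondary endpoint. The central version rests on collected images, so a scan that was not taken cannot be recovered later.

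**Working it through.** **Who is affected.** The parenthesis in 7.2 limits the bullet to participants who stopped study intervention before PD for another reason. The synopsis and 4.1.1.3 keep that same group under CT/MRI, so the conflict with them and with 8.1 holds however the parenthesis is read. The conflict with 7.1.1.1 and the Table 10-5 note is less certain. Those passages concern deterioration that is itself the reason for stopping, and the parenthesis may exclude such participants.

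**What happens to a responder.** Suppose a responder stops treatment for a reason other than PD, has the discontinuation scan without PD, and later progresses clinically.

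1. Under 4.1.1.3 and 8.1, the 6- or 9-weekly scans continue and PD is dated at the next scan that shows it.
2. Under 7.2, scanning stops. By 9.4.1.3 and 10.5.1, DOR is censored at the last scan, before progression, or ends at a later death.

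If the death is counted, the event date is the same as under step 1 or later. If there is no death, an event becomes a censoring and the participant is recorded as still in response. Both shift the estimated distribution towards longer durations or leave it unchanged.

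**Size.** The plan gives no figure to reproduce on this point. Inputs:

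- True median DOR m: 13.8 months (pembrolizumab arm of the second-line phase 3 trial cited in Section 2.2.1) or 9.9 months (post-checkpoint-inhibitor renal trial cited in Section 2.3.2). Both serve as assumptions only.
- Share f of progressions lost: not in the documents, assumed 5-10%.

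With a constant hazard h and a share f of progressions censored instead of counted, the observed hazard is h(1 - f), so the observed median is m/(1 - f):

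- 13.8/0.95 = 14.5 and 13.8/0.90 = 15.3 months.
- 9.9/0.95 = 10.4 and 9.9/0.90 = 11.0 months.

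A Kaplan-Meier simulation (200,000 participants, fixed 6-week scans, 12-24 months of follow-up) gives a similar picture. Its medians move in scan-interval steps of roughly 1.4 months (42/30.4375 = 1.38), so they are coarse.

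- m = 13.8, f = 10%: 13.8 months if kept in follow-up; 15.9 if removed and later deaths are ignored; 15.2 if later deaths count (assumed median survival after progression 4 or 8 months).
- m = 9.9, f = 5% or 10%: 11.0 months in every case, so no visible shift on the scan grid.

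**PFS.** For a true median of 3.0 months, the simulated median stayed at 4.1 months up to f = 20%. The share with an event fell from about 98% to 78% at f = 20% when later deaths were ignored.

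**The case against.** - **Section 7.2 may simply govern.** The opening of Section 7 points to 7.2 for the full list of withdrawal criteria, and 7.2 names other exits that 4.1.1.3 omits (second malignancy, substantial non-compliance, visits harmful to the participant). The silence of 4.1.1.3 alone is therefore weak evidence of a contradiction. That stands. It does not resolve the conflict with 8.1, which separately lists what ends imaging. If 7.2 does govern, the lost scans follow directly.
- **A scan is already required.** When treatment stops without confirmed radiological PD, Section 8.1 says "the investigator should perform a complete physical, laboratory, and radiological assessment as soon as possible". That recovers progression present at that time, so it would be wrong to infer that no objective scan is ever taken. It is triggered by discontinuation and does not cover deterioration arising later in follow-up.
- **Clinical progression might count as an event.** Section 7.1.1.1 allows its use where radiographic evaluation is not possible. Section 6.5.4 counts palliative radiation to a symptomatic solitary lesion or the brain as clinical progression for PFS. Section 9.4.1.3 does not say that progression must be radiological. For PFS this objection stands, because the remaining rules are in SAP v2.0. For DOR it is weaker: 10.5.1 requires objective documentation, and the 7.1.1.1 allowance sits among the criteria for stopping treatment.
- **The consequence is limited.** SAP v3.0 lists DOR without a planned median, and the primary endpoint is ORR. Both are correct, and they bound the importance of the point.

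**Conclusion.** The conflict is real. Section 7.2 ends active follow-up at clinical progression alone for participants off treatment before PD, whereas the synopsis, 4.1.1.3 and 8.1 continue their imaging. Where 7.2 is followed, DOR estimates are longer or unchanged, never shorter. For a true median of 13.8 months and an assumed 5-10% of progressions lost, the illustration is 14.5-15.3 months, with a smaller shift if later deaths count. The actual size cannot be determined from the documents. In the final analysis the effect falls on the listed durations and their censoring flags.

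A reader might infer two stronger conclusions that the documents do not support:

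- *Median DOR inflated to 17-20 months.* That needs 20-30% of all progressions to be lost (13.8/0.80 = 17.3; 13.8/0.70 = 19.7) with later deaths ignored. Section 7.2 reaches only participants already off treatment for a non-PD reason, Section 9.4.1.3 counts deaths, and survival follow-up continues. With later deaths counted, the simulation at f = 20% gives 15.2-16.5 months.
- *PFS shown to be biased upwards.* Its event and censoring rules were not available, one kind of clinical progression does count as an event, and the simulated median did not move up to f = 20%.

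The primary ORR test does not depend on this point.

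**What to change.** - **Protocol.** Reconcile 7.2 with the synopsis, 4.1.1.3, 7.1.1.1 and 8.1 so that clinical progression alone does not end the tumor imaging already scheduled. Keep 7.2's separate exit for visits that would harm the participant. No additional scan is needed. The cost is one line of text.
- **SAP.** State, for DOR and for PFS, whether clinical progression without a scan is an event or a censoring, and at which date. Flag these participants in the DOR listing and in a PFS censoring summary. SAP v3.0 records that recruitment stopped early, so this is the part that can still help: it needs a rule and a flag, and no new data collection if the reason for leaving active follow-up was recorded. SAP v3.0 Section 5.2 already plans to report that reason.
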